### **2.3 Compliance Statement**

This study will be conducted in compliance with Good Clinical Practice (GCP), including the International Conference on Harmonisation (ICH) Guidelines and FDA regulations, consistent with the principles outlined in the Declaration of Helsinki. In addition, the Investigator agrees to adhere to all applicable local laws and regulatory requirements relevant to the use of new therapeutic agents.

The study will be conducted in compliance with the protocol. The appropriate Institutional Review Boards (IRBs) must approve the protocol, any amendments, and the subject informed consent form (ICF) prior to implementation.

Freely given written informed consent must be obtained from every subject prior to participation in this clinical trial. As part of this procedure, the Investigator must explain orally and in writing the nature, duration, and purpose of the study, and the action of the drug in such a manner that the study subject is aware of the potential risks, inconveniences, or AEs that may occur. The study subject should be informed that he/she is free to withdraw from the study at any time. He/she will receive all information that is required by federal regulations and ICH guidelines. The Investigator or designee will provide the Sponsor with a copy of the IRB-approved informed consent form prior to the start of the study. The rights, safety, and well-being of participating subjects are the most important considerations and should prevail over interests of science and society.

Study personnel involved in conducting this trial will be qualified by education, training, and experience to perform their respective task(s). This trial will not use the services of study personnel where sanctions have been invoked or where there has been scientific misconduct or fraud (e.g., loss of medical licensure, debarment).

### 3 STUDY OBJECTIVES

#### 3.1 Primary Objective

The primary objective of this study is to evaluate the safety and tolerability of 5 once-weekly IV infusions of SYNT001 at different dose levels in subjects with chronic pemphigus (vulgaris or foliaceus).

#### 3.2 Secondary Objectives

The secondary objectives of this study are as follow:

- To determine the PK of SYNT001 following 5 once-weekly 1-hour IV infusions at different dose levels
- To assess the effect of 5 once-weekly doses of SYNT001 at different dose levels on the following PD biomarkers:
  - Immunoglobulins: IgG, IgG subtypes (IgG1-4), IgA, IgM
  - Albumin
- To assess the effect of 5 once-weekly doses of SYNT001 at different dose levels on the following disease activity markers:
  - Serum anti-desmoglein (Dsg) (1 and 3) antibody levels
  - Pemphigus Disease Area Index (PDAI)
- To assess immunogenicity (anti-SYNT001 antibodies)

#### 3.3 Exploratory Objectives

The exploratory objectives of this study are as follow:

- To assess the effect of 5 once-weekly doses of SYNT001 at different dose levels on the following biomarkers, including:
  - Serum anti-epithelial cell antibody (AECA) levels by indirect immunofluorescence
  - Circulating immune complexes (CIC)
  - Complement component 3 (C3)
  - Exploratory biomarkers (*FCGR2A* single nucleotide polymorphism-SNP, RNAseq, urine IgG)
  - Immune phenotyping by flow cytometry for CD3+CD4+ T, CD3+CD8+ T, monocytes, NK cells and B cells
  - SYNT001 levels in skin biopsies (optional)
  - Exploratory biomarkers to investigate immune response associated with pemphigus
- To characterize corticosteroid use during the study

## 4 STUDY DESIGN

### 4.1 Study Sites

This study will be conducted at approximately 10 sites in the United States (US).

### 4.2 Study Endpoints

**Primary Outcome Measures:** Assessment of safety data (adverse events [AEs], serious adverse events [SAEs], vital sign measurements, ECGs and clinical laboratory tests) will be the primary safety measure.

### Secondary Outcome Measures

Pharmacokinetics:

- Half-life ( $t_{1/2}$ ), maximum plasma concentration determined directly from the concentration-time profile ( $C_{max}$ ), observed time to reach peak plasma concentration ( $T_{max}$ ), area under the plasma concentration-time curve from pre-dose (time 0) to 24 hours post-dose ( $AUC_{0-24}$ ), and area under the plasma concentration-time curve from pre-dose (time 0) to infinity ( $AUC_{0-\infty}$ )

PD Biomarkers:

- Ig Assessments: Serial assessments of total IgG and IgG subtypes (IgG1-4)
  - Serial assessments of total IgG and IgG subtypes (IgG1-4)
  - IgA levels
  - IgM levels
- Albumin levels

Disease activity markers:

- Serum anti-desmoglein (Dsg) (1 and 3) antibody levels
- Pemphigus Disease Area Index (PDAI) scores

Immunogenicity:

- Anti-SYNT001 antibodies

### Exploratory Outcome Measures

Biomarkers, including:

- CIC
- C3
- Serum AECA levels
- Exploratory biomarkers (*FCGR2A* SNP, RNAseq, urine IgG)

- Immune phenotyping by flow cytometry for measurement of CD3+CD4+ T, CD3+CD8+ T, monocytes, NK cells and B cells
- SYNT001 levels in skin biopsies (optional)
- Exploratory biomarkers to investigate immune response associated with pemphigus

#### Concomitant Treatments

- Corticosteroid use

Further details on the statistical and analytical plan for these endpoints are available in [Section 12](#), Statistical Considerations.

### 4.3 Overview of Study Design

This will be a multicenter, open-label study to assess the safety, tolerability, activity, PK, PD, and immunogenicity of 5 once-weekly IV infusions of SYNT001 to subjects with chronic pemphigus (vulgaris or foliaceus).

Planned doses of SYNT001 to be studied are 10 mg/kg and up to 30 mg/kg. Two cohorts of 8 eligible subjects each will receive 5 once-weekly 60-minute infusions of SYNT001 10 mg/kg or up to 30 mg/kg. Based on review of safety, PD, and clinical outcomes of the first cohort, the dose for the second cohort may be adjusted, but with a maximum dose of 30 mg/kg. Based on review of safety, PD and clinical outcomes from these 2 cohorts, a third cohort of up to 8 subjects may be treated at another dose, with a maximum dose of 45 mg/kg, but may also be lower than 10 mg/kg or between 10 and 30 mg/kg, inclusive.

Cohort	No. of Subjects	Dose
1	8	SYNT001 10 mg/kg
2	8	SYNT001 30 mg/kg

Cohorts will be dosed sequentially beginning with Cohort 1. The first 2 subjects will be dosed at least 24 hours apart. A review of the 24-hour safety data for the first subject will be performed to ensure that there are no overt safety concerns before dosing the second subject. A review of the 7-day safety data for the first 2 subjects will be performed prior to dosing the remaining 6 subjects in the cohort. This evaluation will include a review of AE/SAE reports, vital sign assessments, physical examinations, ECGs and clinical laboratory testing. The seriousness, severity, and relatedness of AEs/SAEs will also be considered in the safety evaluation. Safety data will be reviewed on a continuous basis throughout the study. All data through Day 42

(2 weeks after the last subject's last dose in Cohort 1) will be reviewed before Cohort 2 is initiated. Cohort 2 and Cohort 3, if added, will be dosed per the same schedule.

Safety evaluations will be conducted by a dose escalation committee (DEC). The DEC will consist of the Medical Monitor, an Independent Clinical Expert and a Syntimmune Medical Officer. To assist in the safety assessments, the DEC may request that Investigators, other experts, or members within their organizations review the data and participate in the discussions. Dosing and dose escalation will proceed if the DEC has determined that it would be safe and appropriate to do so. In addition, over the course of the study, the DEC will review any drug-related SAEs to determine if modifications to the study or other measures are necessary to ensure the safety of the subjects.

On days where study drug is administered, vital sign and pulse oximetry measurements will be collected immediately prior to the infusion; 15, 30, and 45 minutes after the start of the infusion; at completion of the infusion; and 30 minutes, 1 hour and 2 hours following completion of the infusion.

On Days 0 and 28, PK blood samples will be collected prior to infusion start and then over the subsequent 48 hours. Subjects will remain at the clinic through the 6-hour PK sample collection and will return to the clinic for the 24- and 48-hour collections. Additional samples will be collected on Days 5 and 33.

On Day 0 photographs will be taken of active lesions. Follow-up photographs will be taken of the same areas on Days 33, 56, 84, and 112. If a subject begins a steroid taper, additional photographs will be taken at the clinic visit during which the decision to begin the taper is made.

Subsequent visits will occur on Days 1, 2, 5, 7, 12, 14, 19, 21, 28, 29, 30, 33, 42 and 56 for safety assessments, study drug dosing, sample collections, and other study procedures.

Subjects also will return to the clinic on Days 84 and 112 for follow-up visits. Subjects whose total IgG is not within 30% of their Day 0 baseline value and not above 500 mg/dL at the Day 112 visit will be referred for further management.

See [Table 1](#) for a schedule of all study events. To assess safety and tolerability, subjects will undergo physical examinations (PEs; including weight), vital sign measurements, clinical (safety) laboratory tests, AE assessments, concomitant medication assessments, and electrocardiograms (ECG).

**Note:** No vaccinations may be given from within 2 weeks of screening through Day 56. Following Day 56, subjects may receive vaccinations at the discretion of the Investigator.

#### **4.4 Randomization and Blinding**

This is an open-label study.

## 5 STUDY POPULATION

### 5.1 Target Population

This study will be conducted in approximately 16 male and female subjects (2 cohorts of 8 subjects each) with a confirmed diagnosis of pemphigus (vulgaris or foliaceus); however, a third cohort of up to 8 subjects may be added. Subjects will be enrolled only once in the study and will not be included in subsequent dosing cohorts. Subjects who withdraw for any reason other than an AE and who do not receive study drug or have only received one dose of study drug may be replaced, up to one subject per cohort. Subjects who do not receive all doses of study drug will continue to be followed through all scheduled visits. The maximum number of subjects who may be enrolled in this study is 27 (24 + up to 3 replacements, as necessary). Within each dosing cohort, no more than 3 subjects may be enrolled with pemphigus foliaceus.

### 5.2 Inclusion Criteria

A subject must meet the following criteria to be eligible for the study:

1. Willing and able to read, understand and sign an informed consent form;
2. Male or female  $\geq$  18 years of age;
3. Documented diagnosis of pemphigus vulgaris or foliaceus based on all 3 of the following criteria:
  - a. Documented clinical history consistent with pemphigus vulgaris or foliaceus (clinical presentation defined as mucosal and/ or skin lesions);
  - b. Presence of Anti-Dsg 1 or 3 antibodies above the upper limit of normal;
  - c. History of at least one positive tissue based test (biopsy, DIF)
4. Active disease: Lesions lasting  $>$  2 weeks, and 3 active lesions in skin or mucosa or 2 active lesions with at least one being a skin lesion  $>$  1 cm diameter:
  - a. If treated with rituximab or other anti-CD20 antibodies, last dose  $>$  12 months prior to screening;
  - b. If being treated with other immunosuppressants (i.e., azathioprine, mycophenolate mofetil or cyclosporine), must be on stable dose ( $<$  10% change in dose) for 6 weeks prior to screening;
  - c. If being treated with corticosteroids, must be  $\leq$  1mg/kg/day of prednisone or equivalent and stable ( $<$  10% change in dose) for 2 weeks prior to screening;

- d. Allowed topical therapies for pemphigus lesions upon entering the study include petroleum jelly or Aquaphor® for the skin or chlorhexidine for the mouth
5. Body mass index (BMI) 18.5 – 39.9 kg/m^2;
6. Has a negative pregnancy test (for women of childbearing potential) documented prior to the first dose of study drug;
7. Females of childbearing potential must agree to be abstinent or else use any two of the following medically acceptable forms of contraception (<1% per year failure rate) from the Screening Period through the final study visit: oral contraceptive, condom with or without spermicidal jelly, diaphragm or cervical cap with spermicidal jelly, or intra-uterine device (IUD). A female whose male partner has had a vasectomy must agree to use one additional form of medically acceptable contraception.
8. Females of non-childbearing potential, defined as surgically sterile (status post hysterectomy, bilateral oophorectomy, or bilateral tubal ligation) or post-menopausal for at least 12 months do not require contraception during the study.
9. Males with female partners of childbearing potential, including males who are surgically sterile (post vasectomy), must agree to be abstinent or else use a medically acceptable form of contraception from the screening period through the final study visit.

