**Table 4: Pharmacodynamic/ Activity Assessments**

Parameter	Collection Timepoints

 
IgG, IgG subtypes (IgG1-4), IgA, IgM
 
	Screening, and Days 0, 1, 2, 5, 7, 12, 14, 19, 21, 28, 29, 30, 33, 42, 56, 84 and 112.

 
Circulating immune complexes (CIC)
 
	Days 0, 5, 7, 12, 14, 19, 21, 28, 33, 42, 56, 84 and 112

 
Albumin
 
	Screening, and Days 0, 7, 14, 21, 28, 33, 42, 56, 84 and 112

 
Anti-Dsg (1 and 3) antibody titer
 
	Screening, Days 0, 7, 14, 33, 56, 84 and 112

 
Complement component 3 (C3)
 
Anti-epithelial cell antibody (AECA) levels by indirect immunofluorescence
 
	Days 0, 14, 33, 56, 84 and 112

 
Exploratory biomarker (RNAseq, Urine IgG)
 
	Days 0, 14, 33, 56, 84 and 112

 
Immune phenotyping by flow cytometry for measurement of CD3+CD4+ T, CD3+CD8+ T, monocytes, NK cells and B cells
 
	Days 0, 28 and 56

 
Exploratory biomarker (FCGR2A SNP, via buccal swab)
 
	Day 0

 
Exploratory pemphigus immune response biomarkers
 
	Days 0, 5, 7, 12, 14, 19, 21, 28, 33, 42, 56, 84 and 112

See [Table 2](#) for timing window allowances with respect to measurement collection. Detailed instructions for sample collection (including collection tubes) and preparation will be provided in a separate laboratory manual.

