## 7 STUDY ASSESSMENTS

### 7.1 Screening Period: Day -14 to Day -1

Informed consent must be obtained before any study-specific samples are taken or study-specific tests or evaluations are conducted. The following assessments at the screening visit are to occur within 14 days before dosing. Study eligibility will be based on satisfying all the study inclusion and exclusion criteria.

At the screening visit, information will be collected and subjects will have clinical evaluations as follows:

- Informed consent ([Section 6.1](#))
- Medical history and demographic data ([Section 6.2](#))
- Review inclusion and exclusion criteria ([Section 5.2](#), [Section 5.3](#))
- Complete PE, including height and weight ([Section 6.3](#))
- Vital sign measurements (after 5 minutes of rest; sitting blood pressure, heart rate, respiratory rate, oral temperature); abnormal results to be repeated after 5 minutes of rest ([Section 6.5](#))
- 12-Lead ECG (to be obtained in triplicate after 5 minutes of rest in the supine position) ([Section 6.6](#))
- Clinical safety laboratory tests (hematology, serum chemistry panel, urinalysis) ([Section 6.7](#))
- Pregnancy test ([Section 6.7](#))
- Hepatitis and HIV screen ([Section 6.7](#))
- PD sample collection ([Section 6.7](#))
  - IgG, IgG subtypes (IgG1-4), IgA, IgM
  - Anti-Dsg (1 and 3) antibody titer
- Concomitant medication assessment ([Section 6.9](#))
- AE assessment ([Section 6.10](#))

### 7.2 Enrollment and First Treatment: Day 0

Study Day 0 is defined as the date the subject is administered their first dose of study drug. On Day 0, subjects will be asked to come to the clinic and the following procedures will be performed prior to the first dose of study drug:

- Complete physical exam ([Section 6.3](#))
- Vital sign measurements (sitting blood pressure, heart rate, respiratory rate, oral temperature); to be measured immediately prior to the infusion ([Section 6.5](#))
- Pulse oximetry (to be measured immediately prior to the infusion) ([Section 6.5](#))

- 
- Clinical safety laboratory tests (hematology, serum chemistry panel, urinalysis) ([Section 6.7](#))
  - Pregnancy test (Section 6.7)
  - Serum tetanus antibody and VZV antibody (Section 6.7)
  - PDAI Score ([Section 6.4](#))
  - PK baseline sample collection (collected just prior to the start of the study drug infusion) (Section 6.7)
  - Immunogenicity sample collection (collected just prior to the start of study drug infusion) (Section 6.7)

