## 10 CONCOMITANT MEDICATION AND TREATMENT

All treatments a subject receives within 14 days prior to enrollment through the end of the study will be documented. Concomitant medication and treatment for co-existing conditions, including those for pemphigus, are permitted if not excluded below. Topical antibiotics are permitted to treat active infections that occur on study. Topical or systemic treatments for oral candidiasis are permitted. Topical lidocaine for transient pain relief is acceptable as needed. Significant increases in anti-pemphigus medications will result in subjects being discontinued from the study. Concomitant treatment that is medically indicated for any AEs the subject experiences during the study are permitted. Premedication is discouraged as prophylaxis against AEs or infusion reactions unless medically indicated from either past medical history, prior infusion reactions or AEs resulting from SYNT001 infusions.

Use of the following treatments will not be permitted during the study unless otherwise specified:

- Rituximab or other anti-CD20 antibody
- Monoclonal antibodies other than study drug
- Any immunosuppressive drugs apart from corticosteroids, azathioprine, mycophenolate mofetil, or cyclosporine.
- Topical steroids
- Any dietary herbal supplements
- Any investigational drug or device
- Any vaccinations through Day 56. Following Day 56, subjects may be vaccinated at the discretion of the Investigator.

If over a period of at least two weeks on study drug, a subject on corticosteroids shows the absence of new lesions and significant healing of lesions that existed at study baseline, a slow corticosteroid taper may be started as per the following suggested schedule

- If on > 30 mg of prednisone per day, decrease by 10 mg every two weeks until a dose of 30 mg per day then decrease by 5 mg every two weeks
- If on < 30 mg of prednisone per day, decrease by 5 mg every two weeks

In cases in which concomitant medications are used, details to be recorded include the following: medication name, start date and time, stop date and time, dose, route, frequency, and reason for use. The concomitant medication names are to be coded using the World Health Organization (WHO) Drug Dictionary (WHO-DD March 2013, Type B2 or later) and classified by anatomical therapeutic chemical (ATC) categories.

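### The stable-dose criteria for corticosteroids and immunosuppressants stop at screening, up to 14 days before the Day 0 baseline, which leaves the PDAI baseline open to a pre-dose treatment change

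*Protocol*

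**What the plan says.** **Stability windows.** Section 5.2, criterion 4c, requires the corticosteroid dose to be stable, with less than "10% change in dose) for 2 weeks prior to screening". Criterion 4b applies the same limit to azathioprine, mycophenolate mofetil and cyclosporine, with less than "10% change in dose) for 6 weeks prior to screening". The Synopsis repeats both.

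**Timing of screening.** Section 7.1 states: "The following assessments at the screening visit are to occur within 14 days before dosing". The period is Day -14 to Day -1. Its list of procedures includes "Review inclusion and exclusion criteria". Table 1 marks that item at screening only, and the Day 0 list in Section 7.2 does not contain it.

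**Baseline.** Section 7.2 says: "Study Day 0 is defined as the date the subject is administered their first dose of study drug". PDAI is first scored on Day 0, before the infusion, and has no screening value. Table 4 schedules anti-Dsg at "Screening, Days 0, 7, 14, 33, 56, 84 and 112", so it has two pre-dose values.

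**Background therapy on study.** Section 10 states: "Significant increases in anti-pemphigus medications will result in subjects being discontinued from the study". It does not define a significant increase or give a day from which the rule applies. It also suggests a corticosteroid taper for subjects who improve over at least two weeks on study drug. Section 8.4.3 provides for stopping further study drug, at the Investigator's discretion.

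**Role of the endpoints.** PDAI and anti-Dsg fall under a secondary objective in Section 3.2: "To assess the effect of 5 once-weekly doses of SYNT001 at different dose levels on the following disease activity markers". The study is open-label with no control arm.

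**The concern.** A stable-dose criterion in an uncontrolled study protects the baseline: it makes it less likely that improvement or worsening after Day 0 comes from a recent change in background treatment. Here the protection ends at the screening visit, while the baseline is taken up to 14 days later. A subject who qualified at screening can have the prednisone dose raised or cut on, say, Day -10 and still satisfy 4c as written.

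If the dose was raised, part of the later fall in PDAI may belong to the corticosteroid and would be read as a SYNT001 effect. If it was cut, the resulting worsening could mask an effect. With no concurrent control and 8 subjects per cohort, a cohort summary cannot separate the two sources.

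Clinical outcomes also feed decisions. Sections 4.3 and 6.8 name them among the grounds for proceeding to, or adjusting, Cohort 2 and for choosing a Cohort 3 dose.

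**Working it through.** The protocol gives no sample size calculation and no figure for this point, so there is nothing to reproduce. The check is date arithmetic, a reading of the provisions that might close the gap, and an illustration on assumed values.

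**1. The gap.** With screening on Day -14, the distance to first dose is 0 - (-14) = 14 days. With screening on Day -1 it is 1 day. The gap is therefore 1 to 14 days, and at its longest it equals the whole 2-week corticosteroid window.

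**2. Assured stability up to Day 0.** A change made at any time after the screening visit is outside both windows. The stable interval that the criteria guarantee immediately before Day 0 is 0 days for both drug classes.

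**3. Could another provision close the gap?**

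| Provision | Pre-dose increase | Pre-dose decrease |
|---|---|---|
| Section 10, significant increases | Possibly, if judged significant; undefined and looser than the <10% limit | Not addressed |
| Section 10, suggested taper | Not addressed | Describes a reduction only after at least two weeks on study drug |
| Section 8.4.3 | Stops further study drug, so acts once dosing has begun | Not addressed |
| Day 0 medication assessment (Section 7.2) | Records it | Records it |

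None carries the <10% limit from screening to first dose. The protocol does extend other rules when it means to: vaccinations are barred from within 2 weeks of screening through Day 56, and contraception runs from the Screening Period to the final visit.

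**4. Does the Day 0 value absorb the change?** Assume a first-order onset with half-time *h* and a change made *a* days before Day 0. The share of its full effect that appears between Day 0 and Day 33 is

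2^(-a/h) - 2^(-(a+33)/h).

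The protocol gives no *h*. Values of 7, 14 and 28 days are an assumed range.

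| Change on | h = 7 | h = 14 | h = 28 |
|---|---|---|---|
| Day -13 | 27% | 42% | 40% |
| Day -7 | 48% | 57% | 47% |
| Day -1 | 87% | 77% | 54% |

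Worked example, Day -7 and h = 7: 2^(-1) - 2^(-40/7) = 0.500 - 0.019 = 0.48.

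Under these assumptions, roughly a quarter to nearly nine tenths of the change's effect falls after baseline.

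**5. With the limit carried to Day 0.** The stable interval would be at least 14 + 1 = 15 days for corticosteroids and 42 + 1 = 43 days for immunosuppressants (screening on Day -1). It would be 28 and 56 days with screening on Day -14. The same formula bounds what remains. A change at Day -14 leaves 24%, 40% and 39% for h = 7, 14 and 28; a change at Day -42 leaves 2%, 10% and 20%. Carry-over is reduced but not abolished, chiefly for corticosteroids.

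**The case against.** The best case against is that the protocol limits the problem in several ways, and most of these points stand.

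- **Large increases may be caught.** The Section 10 rule has no start day, and Sections 5.1 and 8.3 foresee withdrawing and replacing subjects who have not been dosed. A big pre-dose increase could therefore remove the subject. Smaller increases that still exceed the <10% limit remain open.
- **Decreases are not wholly ignored.** A reader might infer that Section 10 is silent on reductions. It is not, since it suggests a taper. That taper is tied to time on study drug, however, so it says nothing about a cut between screening and Day 0.
- **Anti-Dsg has a screening value.** A reader might treat it as equally exposed. Its two pre-dose values bracket the gap, so a shift under way can be partly seen. PDAI has no such check.
- **There is other activity evidence.** PDAI and anti-Dsg are not the only evidence. Table 4 also lists IgG and its subtypes, circulating immune complexes, C3 and AECA, and there are cohorts at different doses, although not randomised.
- **The change is recorded.** Treatments are documented from 14 days before enrollment with dose and dates, and Section 7.2 places enrollment on Day 0. The record therefore spans the gap, and the documents do not show that the exploratory corticosteroid-use objective is distorted. Recording reveals a change but does not prevent it.
- **Anchoring to screening is a convention here.** The washouts in Section 5.3 use the same anchor. That explains the wording but does not extend the stability limit to baseline.

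**Conclusion.** The gap is in the text, and its length, up to 14 days, follows from the protocol's own dates. It mainly affects PDAI, a secondary endpoint with a single pre-dose value and no control. Anti-Dsg is less affected, and the primary safety objective little.

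The size of any bias cannot be computed from the protocol, and its direction is open. The percentages in the working rest on assumed half-times. They show only that the Day 0 score need not absorb a recent change.

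A reader might infer that the activity results would be materially inflated. The documents do not support that. An example makes the point: suppose one of 8 subjects improves by 80% because of a corticosteroid change and the other 7 improve by 20%. The mean becomes (80 + 7 × 20)/8 = 27.5% instead of 20%. But those inputs are invented, the median stays at 20%, and the planned minimum and maximum and the listings would expose the outlier.

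This is a cheap improvement of modest severity.

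**What to change.** In criteria 4b and 4c, in both Section 5.2 and the Synopsis, extend the protocol's own <10% stability limit so that it runs from the existing window before screening through the first dose on Day 0. Add that compliance is verified at the Day 0 pre-dose concomitant medication assessment, which Section 7.2 already schedules.

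This adds no visit, sample or new threshold, and the dose data are already collected. The cost is one phrase in two sub-criteria, in two places, and an occasional screen failure when a dose changes during the screening period.
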